## 4.10 Potential risks of study products and administration

**Table 4-7 Summary of potential risks of study products and administration**

Common	
 
Mild to moderate injection site pain, tenderness, erythema, or swelling/induration/edema
 
Malaise/fatigue, myalgia, or headache in the first few days following injection
 
A vaccine-induced positive HIV antibody test result
 

Less common	
 
Severe injection site pain or tenderness
 
Fever, chills, flu-like syndrome, arthralgia, rash, decreased appetite, nausea, or dizziness in the first few days following injection
 
Vasovagal reaction/lightheadedness/dizziness related to the injection procedure
 
Transient changes in clinical laboratory values
 
Injection site hematoma, bruising/ecchymosis, other transient lesions, itching, or bleeding related to the injection procedure
 

Uncommon or rare	
 
Severe localized injection site reaction, such as sterile abscess or secondary bacterial infection
 
Allergic reaction, including rash, urticaria, angioedema, bronchospasm, or anaphylaxis
 
Muscle damage at the injection site
 

Theoretical risks	
 
Autoimmune disease
 
Effects on a participant's response to an approved HIV vaccine administered in the future
 
Effects on susceptibility to HIV, if the participant is exposed to HIV
 
Effects on the course of HIV infection/disease, if the participant is infected with HIV
 
Effects on the fetus and on pregnancy
 

## 5 Objectives and endpoints

### 5.1 Primary objectives and endpoints

*Primary objective 1:*

To evaluate and compare the safety and tolerability of the CH505TF gp120 proteins produced by transient and stable transfection in HIV-1-uninfected, healthy adults

*Primary endpoint 1:*

Local and systemic reactogenicity signs and symptoms, laboratory measures of safety, and AEs and SAEs

*Primary objective 2:*

To evaluate and compare the magnitude of binding antibody responses elicited by the CH505TF gp120 proteins produced via transient and stable transfection methods

*Primary endpoint 2:*

HIV-specific total IgG binding antibody responses against the homologous proteins, as assessed by BAMA at peak timepoint (2 weeks after 3rd vaccination)

### 5.2 Secondary objectives and endpoints

*Secondary objective 1:*

To evaluate and compare the breadth and kinetics of binding antibody responses elicited by the CH505TF gp120 proteins produced via transient and stable transfection methods

*Secondary endpoint 1:*

HIV-specific total IgG binding antibody responses against the homologous proteins and magnitude-breadth (M-B) measures against panels of cross-clade Env proteins and of cross-clade V2 proteins, as assessed by BAMA at peak timepoints (2 weeks after the 2nd and 3rd vaccinations) and late timepoints (3 and 6 months after the 3rd vaccination)

*Secondary objective 2:*

To evaluate and compare the IgG subclass and IgA binding antibody responses elicited by the CH505TF gp120 proteins produced via transient and stable transfection methods

*Secondary endpoint 2:*

HIV-specific IgG subclass and IgA binding antibody response rates and magnitudes against homologous Env and V2 proteins, as assessed by BAMA at 2 weeks after the 2nd vaccination, 2 weeks after the 3rd vaccinations, and 3 and 6 months after the 3rd vaccination

*Secondary objective 3:*

To evaluate the ability of the two CH505TF gp120 proteins to elicit HIV-specific neutralizing antibodies (nAbs)

*Secondary endpoint 3:*

Magnitude and breadth of nAb responses against a panel of viral isolates as assessed by area under the M-B curves 2 weeks after the 2nd and 3rd vaccinations

*Secondary objective 4:*

To evaluate the avidity of antibody responses elicited by the CH505TF gp120 proteins

*Secondary endpoint 4*

Avidity of Env-specific IgG antibodies at baseline and 2 weeks after the 3rd vaccination

*Secondary objective 5:*

To evaluate HIV-specific T-cell responses induced by the two CH505TF gp120 proteins

*Secondary endpoint 5:*

Response rate, magnitude, and polyfunctionality of CD4+ T-cell responses as assessed by intracellular cytokine staining (ICS) assays 2 weeks after the 2nd and 3rd vaccinations

### **5.3 Exploratory objectives**

*Exploratory objective 1:*

To evaluate the ability of the two CH505TF gp120 proteins to elicit memory B cells that differentially bind wildtype CH505 gp120Env vs mutant CH505 Env IΔ371 gp120

*Exploratory objective 3:*

To characterize the BCR repertoire of HIV-specific B cells

*Exploratory objective 4:*

To further evaluate vaccine immunogenicity, additional immunogenicity assays may be performed, including on samples from other timepoints, based on the HVTN Laboratory Assay Algorithm

*Exploratory objective 5:*

To conduct analyses related to furthering the understanding of HIV, immunology, vaccines, and clinical trial conduct

## 6 Statistical considerations

### 6.1 Accrual and sample size calculations

Recruitment will target enrolling 30 healthy, HIV-uninfected adult participants aged 18 to 50 years.

#### 6.1.1 Sample size calculations for safety

The goal of the safety evaluation for this study is to identify safety concerns associated with product administration. The ability of the study to detect SAEs ([Table 6-1](#)) can be expressed by the true event rate above which at least 1 SAE would likely be observed and the true event rate below which no events would likely be observed. Specifically, for each vaccine arm of the study ( $n = 15$ ), there is a 90% chance of observing at least 1 event if the true rate of such an event is 15% or more; and there is a 90% chance of observing no events if the true rate is 0.5% or less. As a reference, in HVTN vaccine trials from December 2000 through April 2014, about 4% of participants who received placebos experienced an SAE.

Probabilities of observing 0, 1 or more, and 2 or more events among arms of size 15 are presented in [Table 6-1](#) for a range of possible true AE rates. These calculations provide a more complete picture of the sensitivity of this study design to identify potential safety problems with the vaccine.

**Table 6-1 Probability of observing 0 events, 1 or more events, and 2 or more events, among arms of size 15, for different true event rates**

True event rate (%)	Pr(0/15)	Pr(1+/15)	Pr(2+/15)
0.5	0.928	0.072	0.003
1	0.860	0.140	0.010
4	0.542	0.458	0.119
10	0.206	0.794	0.451
15	0.087	0.913	0.681
20	0.035	0.965	0.833
30	0.005	0.995	0.965
40	0.000	1.000	0.995

An alternative way of describing the statistical properties of the study design is in terms of the 95% confidence interval (CI) for the true rate of an AE based on the observed data. [Table 6-2](#) shows the 2-sided 95% CIs for the probability of an event based on a particular observed rate. Calculations are done using the score test method (50). If none of the 30 participants receiving a vaccine regimen experience a safety event, the 95% 2-sided upper confidence bound for the true rate of such events in the total vaccinated population ( $n = 30$ ) is 11.4%. For each individual vaccine arm ( $n = 15$ ), the 2-sided upper confidence bound for this rate is 20.4%.

**Table 6-2 Two-sided 95% CIs based on observing a particular rate of safety endpoints for sample sizes 15 and 30**

Observed event rate	95% CI (%)
0/15	[0.0, 20.4]
1/15	[0.3, 29.8]
2/15	[3.7, 37.9]
0/30	[0.0, 11.4]
1/30	[0.2, 16.7]
2/30	[1.8, 21.3]

### 6.1.2 Sample size calculations for immunogenicity

Binding antibodies will be measured by geometric mean fluorescence intensity (FI) for homologous proteins. We will test the null hypothesis that the geometric mean FI in the transient arm is less than 1/4 of the geometric mean FI in the stable arm. The power to reject this null hypothesis depends on the variability of the binding antibodies measurements and sample sizes. Based on HVTN 505 data, the standard deviation of the natural log of geometric mean FI at the dilutions optimized for immune correlates analyses, which maximize the proportion of samples within the linear range of the dilution-response curve, is around 1.4. Table 6-3 lists the power under a range of standard deviations, non-inferiority margins, and sample sizes.

The power study assumes that  $\log_e$ (geometric mean FI for a panel of Envs) is normally distributed and has the same spread in both arms. We will form a 95% confidence interval for the difference in  $\log_e$ (FI)s between the transient arm and the stable arm and compare the lower confidence interval to  $\log_e(1/4)$ . Under the parameters of the proposed study, the estimated power to reject the null hypothesis ranges from 0.86 to 0.63 for standard deviation ranging from 1.2 to 1.6.

**Table 6-3 Power to reject the null hypothesis that the geometric mean FI in the transient arm is less than non-inferiority margin of the geometric mean FI in the stable arm.** Standard deviation: spread of  $\log_e$ (FI); n: sample size for each arm. The alpha level is set at 0.05 for a two-sided test.

Standard Deviation	Non-inferiority Margin																				
	1/8			1/4			1/2			1/8			1/4			1/2					
	n = 10			n = 15			n = 20			n = 10			n = 15			n = 20					
1.2			0.96		0.69		0.23				1.00		0.86		0.33		1.00		0.95		0.43
1.4			0.88		0.55		0.18				0.98		0.74		0.26		1.00		0.86		0.33
1.6			0.78		0.45		0.15				0.93		0.63		0.21		0.98		0.76		0.27

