#### 4.5 Trial design rationale

This is a double-blind, randomized clinical trial, which will compare the safety and immunogenicity of a CH505TF gp120 produced via stably transfected cell lines compared with production via transiently transfected cell line. Fifteen healthy, HIV-1-uninfected adults will be enrolled into each group, vaccinated at months 0, 2, and 6, and followed for a total of 12 months. The design of this comparative study is intended to allow rapid assessment of the comparability of the Env proteins in terms of safety, tolerability, and immunogenicity. It is likely that antibody responses to the Env proteins will peak after the 3rd injection given at month 6. Assessments of humoral immune responses are planned at early, peak, plateau, and late timepoints by analyzing binding to a panel of Env antigens using the binding antibody multiplex assay (BAMA). From an immunogenicity perspective, this study design will allow us to assess both magnitude and breadth of humoral immune responses as well as understand in detail the kinetics of the antibody responses.

The overarching goal of this study is to demonstrate whether immunization with Env protein produced by transiently transfected cells is as safe and immunogenic as immunization with Env produced by stably transfected cells. While past vaccine trials of Env proteins (Envs) have used Envs made by stable transfection, much of the early animal research is performed using Envs produced by transient transfection. Envs made by both approaches have been safe and immunogenic in animal studies, and are analytically similar (Section 4.4), but HIV Envs made by transient transfection have not yet been tested in clinical trials. By directly comparing CH505TF gp120 produced by transiently transfected cells with CH505TF gp120 produced by stably transfected cells this study has the potential to enable future clinical trials with novel Env immunogens to launch much faster.

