#### **4.5.2 Schedule**

Vaccinations will occur at months 0, 2, and 6. These immunization intervals were chosen based on prior studies with different Env proteins and are likely to lead to high peak antibody titers and high humoral response rates after the third vaccination. In previous trials with adjuvanted protein vaccines, peak immunogenicity has been observed after 3 doses of the protein, while a prolonged rest period between the 2nd and 3rd vaccinations is thought to enhance antibody maturation.

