Samples from post-enrollment visits were declared to have positive responses if they met three conditions: (1) the MFI minus Blank values were  $\geq$  antigen-specific cutoff at the 1:50 dilution level for IgG (based on the 95th percentile of baseline samples as calculated by SAS PROC UNIVARIATE default method, and at least 100 MFI minus Blank), (2) the MFI minus Blank values were greater than 3 times the baseline (day 0) MFI minus Blank values, and (3) the MFI values were greater than 3 times the baseline MFI values.

Net MFI (MFI minus Blank) were truncated at 22,000, the upper limit of the linear range of the assay. Additionally, samples were excluded from threshold calculation and analysis if the baseline analyte net MFI exceeded 6500. For each combination of individual and antigen the area under the titration curve (AUC) at each time point was calculated over dilutions [insert dilution factors of the titration series] using the trapezoidal integration, with base 10 log-transformation of the dilutions and with truncation at zero in the case of negative net MFI values and no ceiling (at 22,000) truncation.

Tables show positive response rates and corresponding 95% confidence intervals calculated by the Wilson score method [1], as well as summary statistics among positive responders and all participants.

Barnard's test was used to compare response rates between treatment groups, while the Wilcoxon rank sum test was used to compare response magnitudes between treatment groups, among positive and negative responders, and among the subset of positive responders. Response magnitude comparisons among positive responders will not be done if there are fewer than 5 responders per treatment group.

Net MFI responses at the 1:50 dilution level and the titers (AUC) were used to summarize the magnitude at a given time-point. These distributions are displayed graphically by treatment arm. Plots include data from responders in color and non-responders in gray, with box plots based on

data from responders superimposed on the distribution. Data points for each participant are connected by a gray line. The mid-line of the box denotes the median and the ends of the box denote the 25th and 75th percentiles. The whiskers that extend from the top and bottom of the box extend to the most extreme data points that are no more than 1.5 times the interquartile range (i.e., height of the box) or if no value meets this criterion, to the data extremes.

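### The SAP omits the protocol's 1/4 non-inferiority test and plans a Wilcoxon test of no difference instead, with no rule for which analysis governs

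*Protocol*

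**What the plan says.** Protocol 4.5 gives the goal as showing whether immunization with the transiently produced protein "is as safe and immunogenic as immunization with Env produced by stably transfected cells". Primary objective 2 (Protocol 5.1) is to evaluate and compare binding antibody magnitude, with total IgG to the homologous proteins two weeks after the third vaccination as its endpoint.

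Protocol 6.1.2 is the only place with a numerical criterion for that comparison. What it tests is this: "null hypothesis that the geometric mean FI in the transient arm is less than 1/4 of the geometric mean FI in the stable arm". Its decision step is to form a 95% confidence interval for the difference in log_e(FI) and "compare the lower confidence interval to" log_e(1/4). The error rate is fixed: "The alpha level is set at 0.05 for a two-sided test". For 15 per arm it reports that "the estimated power to reject the null hypothesis ranges from 0.86 to 0.63 for standard deviation ranging from 1.2 to 1.6".

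The analysis sections do not carry this forward. Protocol 6.4.4.1 and SAP section 9 compare mean or median readouts between arms with bootstrap intervals and name no margin. For the binding antibody assay, SAP 9.3 says that "the Wilcoxon rank sum test was used to compare response magnitudes between treatment groups". The tables in SAP 9.3.1 list Barnard and Wilcoxon comparisons of T1 and T2 at visits 2 and 7, for net MFI and AUC. None is a ratio interval set against 1/4. The SAP's modification history describes version 1.0 as covering this assay, so nothing suggests that the test is held over for a later version.

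**The concern.** A test of no difference and a non-inferiority test answer different questions. A non-significant Wilcoxon result does not show that a fourfold loss has been excluded, and a significant one does not show that the loss is as large as fourfold. If the SAP is followed as written, the hypothesis on which the trial was sized is never tested. The reader is left with a p-value that, in a trial of 30, can easily be taken as evidence that the two products are alike.

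The result is meant to support faster entry of transiently produced Env proteins into later trials (Protocol 4.5 and 4.6). With two analyses on file and no order between them, the choice of which to report can be made after the data are seen.

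**Working it through.** **Inputs.** n = 15 per arm (Protocol Table 3-1). Margin 1/4, so ln(1/4) = −1.386 (6.1.2). Two-sided alpha 0.05 (6.1.2). Planning SD of log_e(FI): 6.1.2 takes it from another trial, HVTN 505, at dilutions "which maximize the proportion of samples within the linear range of the dilution-response curve, is around 1.4"; the planned range is 1.2 to 1.6. Normal log_e(FI) with equal spread in both arms (6.1.2). The true ratio behind the stated power is not given; 1 is inferred because it reproduces the table.

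**The plan's own power.** SE = SD × √(2/15), df = 28, critical value t = 2.048, noncentrality δ = (ln R − ln(1/4))/SE for true ratio R, and power = P(noncentral t with df 28 and δ > 2.048).

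- SD 1.4: SE = 1.4 × 0.3651 = 0.511. With R = 1, δ = 1.386/0.511 = 2.71, and power = 0.745.
- SD 1.2 / 1.4 / 1.6 gives 0.863 / 0.745 / 0.630, against 0.86 / 0.74 / 0.63 in Table 6-3. All 27 cells of that table agree within 0.02.

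**Chance of excluding 1/4 at SD 1.4.** Same formula: 0.745 with no loss, 0.457 with a true 1.5-fold loss, 0.258 with a true twofold loss, 0.025 with a true fourfold loss.

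**What the Wilcoxon test would show.** Trials were simulated at n = 15 per arm with normal log_e(FI) and SD 1.4. The two-sided 5% Wilcoxon test and the t-based 95% interval were applied to the same data.

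| True loss | Result | Share of trials |
|---|---|---|
| Fourfold | Wilcoxon not significant | about 29% |
| Twofold | Wilcoxon not significant, 1/4 not excluded | about 51% |
| None | Wilcoxon not significant, 1/4 not excluded | about 23% |

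A hand check uses the t-test, which has slightly more power here.

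- A fourfold loss is as far from a ratio of 1 as 1 is from 1/4, so the t-test of no difference misses it in 1 − 0.745 = 25.5% of trials.
- A twofold loss lies midway on the log scale. Not excluding 1/4 has probability 1 − 0.258 = 0.742 and being significantly lower has 0.258. The two findings of excluding 1/4 and being lower almost never coincide at this SD, so the remainder is 0.742 − 0.258 = 0.484.
- With no loss, the remainder is 0.255 − 0.025 = 0.230.

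The simulated Wilcoxon figures sit at or slightly above these.

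**The opposite conflict.** A 95% interval lies wholly between 1/4 and 1 only if its full width is below ln 4. That requires an observed SD below ln 4/(2 × 2.048 × √(2/15)) = 1.386/1.496 = 0.93. If the true SD is 1.4, the observed SD falls below 0.93 in about 0.4% of trials. For a true twofold loss, both findings occur together in under 0.1% of trials at SD 1.4 and about 0.4% at SD 1.2.

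**Significantly lower results at the planning SD.** The half-width at an observed SD of 1.4 is 2.048 × 0.511 = 1.047. An upper limit below 1 then needs an observed ratio below exp(−1.047) = 0.35, which puts the lower limit below exp(−2.094) = 0.12. At that SD, every significantly lower result also fails the 1/4 criterion. Reporting it only as non-inferiority not shown would hide the finding. With a true twofold loss this affects about 26% of trials.

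**The case against.** The protocol's commitment in 6.1.2 is explicit and the SAP does not withdraw it, so an analyst could still compute the interval. The bootstrap intervals in SAP section 9 come close to it. This stands in part: the needed data and most of the machinery are already planned. But the SAP fixes no log scale, ratio or margin for those intervals, its table list does not contain the comparison, and it ranks nothing.

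It is also fair to say that the two tests address different questions, so differing results are not a contradiction. That is correct, and it is the reason a deciding analysis has to be named.

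A reader might infer stronger points, which the documents do not support.

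- **The rule is lax because a true 1.5-fold loss passes 46% of the time at SD 1.4.** That loss lies inside the 1/4 margin, so 46% is not an error rate, and 1.5-fold is an illustration that appears nowhere in the documents. At the margin the error is 0.025. At an observed SD of 1.4 the observed ratio must reach 0.25 × exp(1.047) = 0.71 to pass.
- **Results both non-inferior and significantly lower should be expected.** They need an SD below the planned range. Protocol 4.5.2 calls the schedule "likely to lead to high peak antibody titers and high humoral response rates after the third vaccination", which concerns level, not spread. The SAP's ceiling of 22,000 on net MFI might compress the spread, but no SD for that readout is given. This remains a conditional risk.
- **Only excluding a twofold loss should count as equally immunogenic.** The documents give no reason for 1/4, but they give none for 1/2 either. By Table 6-3, using 1/2 would cut the chance of the claim for identical products from 0.74 to 0.26 at SD 1.4. Nor does any section say that clearing 1/4 earns that label; Protocol 4.5 states a goal.

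**Conclusion.** The concern holds as a mismatch between the two documents. The protocol's primary immunogenicity hypothesis is absent from the SAP's binding antibody analysis, and no rule says whether the interval or the Wilcoxon test governs. It matters within the planned SD range: about 29% of trials with a true fourfold loss would give a non-significant Wilcoxon result, and about half of trials with a true twofold loss would give no significant difference while leaving a fourfold loss open. The stated power is correct for the test in 6.1.2.

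These figures assume 15 evaluable participants per arm, normal log_e(FI) with a common SD of 1.4, no effect of the net MFI ceiling, and a t-based interval. The immunogenicity analysis is per-protocol and the sample size makes no allowance for losses; fewer evaluable participants would widen the interval and reduce the power of both tests.

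**What to change.** In SAP 9.3, for homologous total IgG at visit 7, add the 95% CI for the Transient/Stable geometric mean ratio, compared with 1/4, as the deciding primary analysis, and label the Wilcoxon test supportive. Add the matching line to the tables in 9.3.1. Say whether the interval is t-based on log_e values, which is what the stated power assumes, or bootstrap, and which readout and homologous antigen it uses.

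Fix the reading of the interval in advance:

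- Lower limit above 1/4: a fourfold or greater loss is ruled out. Claim no more than that.
- Lower limit at or below 1/4: a fourfold loss is not ruled out.
- In every case, report both limits. Whenever the upper limit is below 1, state that the Transient arm is lower, including when the lower limit is at or below 1/4.
- Whether a twofold loss is excluded may be reported descriptively from the same interval.

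The cost is a few sentences and one extra interval. Sample size, margin, alpha and stated power do not change.

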## **6.2 Randomization**

A participant's randomization assignment will be computer-generated and provided to the HVTN CRS pharmacist through a Web-based randomization system. At each institution, the pharmacist with primary responsibility for dispensing study products is charged with maintaining security of the treatment assignments (except in emergency situations as specified in the HVTN MOP).

